## 10.5 CLINICAL EVALUATION OF LIVER INJURY

Alterations of liver laboratory parameters, as described in [Section 5.3.6](#) (AESIs), are to be further evaluated using the following procedures.

Repeat the following laboratory tests: ALT, AST and bilirubin (total and direct) within 48 to 72 hours and provide the additional blood sample to the central laboratory for automatic reflex testing of the below listed laboratory parameters.

Only in cases whereby the central laboratory is not immediately available (e.g. if the logistics are such that the patient's repeat specimen would not reach the central laboratory in a reasonable timeframe), ALT, AST and bilirubin (total and direct) will be evaluated by a local laboratory and the results made available to the Investigator and to Boehringer Ingelheim as soon as possible. If in such a case it is confirmed that ALT and/or AST are  $\geq 3$  times ULN combined with an elevation of total bilirubin  $\geq 2$  times ULN, results of the laboratory parameters described below must be made available to the Investigator and to Boehringer Ingelheim as soon as possible.

In addition:

- Obtain a detailed history of current symptoms and concurrent diagnoses and medical history according to the "DILI checklist" provided in the ISF
- Obtain history of concomitant drug use (including non-prescription medications, herbal and dietary supplement preparations), alcohol use, recreational drug use, and special diets according to the "DILI checklist" provided in the ISF
- Obtain a history of exposure to environmental chemical agents (consider home and work place exposure) according to the "DILI checklist" provided in the ISF

and report these via the eCRF.

The Investigator is to follow the laboratory testing and assessments as noted in the DILI checklist in the ISF. These assessments include but are not limited to:

### *Clinical chemistry*

- Alkaline phosphatase, albumin, prothrombin time or International Normalized Ratio, creatine kinase, creatine kinase muscle-brain, coeruloplasmin,  $\alpha$ -1 antitrypsin, transferin, amylase, lipase, fasting glucose, cholesterol, triglycerides, cholinesterase

### *Serology*

- Hepatitis A (Anti-IgM, total Ig), hepatitis B (hepatitis B surface antigen, antiHBs, DNA), hepatitis C (antiHCV, RNA if antiHCV positive), hepatitis D (anti-IgM, total Ig), hepatitis E (antihepatitis E virus [HEV], antiHEV IgM, RNA if antiHEV IgM positive), antiSmooth Muscle antibody (titer), antinuclear antibody (titer), antiliver-kidney microsomes antibody, antimitochondrial antibody, Epstein Barr Virus (virus capsid antigen [VCA] IgG, VCA IgM), cytomegalovirus (IgG, IgM), herpes simplex virus (IgG, IgM), varicella (IgG, IgM), parvovirus (IgG, IgM), toxoplasmosis (IgG, IgM)

### *Hormones, tumor marker*

- Thyroid stimulating hormone

*Hematology*

- Complete blood count (including differential counts)

Provide abdominal ultrasound to rule out biliary tract, pancreatic or intrahepatic pathology, e.g. bile duct stones or neoplasm.

Initiate close observation of patients by repeat testing of ALT, AST, and total bilirubin (with fractionation by total and direct) at least weekly until the laboratory ALT and or AST abnormalities stabilize or return to normal, then according to the protocol. Depending on further laboratory changes, additional parameters identified e.g. by reflex testing, will be followed up based on medical judgment and GCP.

## 11. DESCRIPTION OF GLOBAL AMENDMENT(S)

|  |  |  |
|--|--|--|
| Number of global amendment  |  | 01   |
| Date of CTP revision  |  | 19. February 2016  |
| EudraCT number  |  | 2015-002634-41   |
| BI Trial number   |  | 1297.3   |
| BI Investigational Product(s)   |  | BI695501   |
| Title of protocol   |  | Long-term assessment of safety, efficacy, pharmacokinetics and immunogenicity of BI 695501 in patients with rheumatoid arthritis (RA): an open-label extension trial for patients who have completed trial 1297.2 and are eligible for long-term treatment with adalimumab |
| To be implemented only after approval of the IRB / IEC / Competent Authorities  |  |   |
| To be implemented immediately in order to eliminate hazard – IRB / IEC / Competent Authority to be notified of change with request for approval |  |    |
| Can be implemented without IRB / IEC / Competent Authority approval as changes involve logistical or administrative aspects only                |  |    |
| Section to be changed   |  |  |
|  |  | Clinical Trial Protocol Synopsis - Trial Clinical Monitor   |
| Description of change   |  | Change of the name and contact details (phone and fax number) regarding the Trial Clinical Monitor from _____ to _____.  |
| Rationale for change  |  | The responsibility as Trial Clinical Monitor for this trial has been transferred.  |
| Section to be changed   |  |  |
|  |  | Clinical Trial Protocol Synopsis - Flow Chart   |
| Description of change   |  | The following three changes are made to the flow   |

|                              |  |  |
|------------------------------|--|--|
|                              |  | 
chart:
 
 
1. Change of the permitted visit window for the Screening Visit from <math>\pm 1</math> day to <math>\pm 3</math> days.
 
2. Inclusion of the following sentence in the footnotes:
 ‘VAS assessments and completion of the HAQ-DI and SF-36 v2 questionnaires must be done prior to any visit procedures at this day. Patient questionnaires completed for the 1297.2 trial will be used as baseline questionnaires for the 1297.3 trial.’
 
3. Inclusion of the following footnote regarding ECG:
 ‘Two consecutive recordings need to be taken.’
 
 |
| Rationale for change  |  | 
Ad 1) The visit window for the screening visit for study 1297.3 is changed to <math>\pm 3</math> days to be in line with the permitted visit window for the End of Treatment Visit (Week 48) of the parent trial 1297.2, as these two visits coincide.
 
Ad 2) Emphasis of the order of the assessments to be performed at the visits to avoid that the patients are biased before doing the questionnaires.
 
Ad 3) Emphasis that in study 1297.3 two ECGs are to be taken (as in the parent study 1297.2).
  |
| Section to be changed |  | 3.3.3: Exclusion Criteria   |
| Description of change |  | 
Deletion of exclusion criteria #2
 
Original text:
 
Patients with major protocol deviations in Trial 1297.2
  |
| Rationale for change  |  | 
The term “major protocol deviations” was not further defined in the clinical study protocol (CTP). The vast majority of currently known major protocol deviations is of administrative nature and not relevant for safety of the patients. As judged by BI, these administrative deviations do not justify exclusion of patients who would be otherwise eligible for participation in 1297.3 based on the clinical and safety assessments performed at the screening/baseline visit and are expected to have a continued benefit from further treatment in the 1297.3 study.
  |

|                              |  |  |
|------------------------------|--|--|
|                              |  | Patients having any major protocol violations in study 1297.2 related to safety will be excluded from the study 1297.3 based on the other specific exclusion criteria listed in the CTP.   |
| Section to be changed |  | 5.2.1 Joint assessments   |
| Description of change |  | 
Correction of the text regarding training of independent joint assessor
 
Original text:
 
Wherever possible, the same person will perform the joint assessment throughout the trial (i.e., for all patients at each trial site). Standardized training will be provided to the independent joint assessor during the Investigator Meeting via the training portal. This training will be documented and filed in the ISF.
 
Amended text:
 
Wherever possible, the same person will perform the joint assessment throughout the trial (i.e., for all patients at each trial site). Standardized training will be provided to the independent joint assessor via the training modules provided in the specific study portal. This training will be documented and filed in the ISF.
 |
| Rationale for change  |  | The original CTP states that standardized training will be provided to the independent joint assessor (IJA) during the Investigator Meeting via the training portal. Based on the fact that no investigator meeting will take place for this extension study, training of the IJAs will be conducted via the respective training modules posted in the study portal.   |
| Section to be changed |  | 5.4.2 Methods of sample collection  |
| Description of change |  | 
Revision of wording regarding storage of PK samples
 
Original text:
 
After completion of the trial, selected PK samples may be retained and used for further methodological investigations, e.g., stability testing. The PK samples will be discarded after the completion of the additional investigations and after the Sponsor has approved this in writing, but not earlier than 5 years after the final Clinical Trial
  |

|                              |  |   |
|------------------------------|--|---|
|                              |  | 
Report (CTR) has been signed.
 
Amended text:
 
After completion of the trial, selected PK samples may be retained and used for further methodological investigations, e.g., stability testing. The PK samples will be discarded after the completion of the additional investigations upon the Sponsor's written approval. The PK samples may be destroyed 5 years after the final Clinical Trial Report (CTR) has been signed, and in accordance with local regulation.
   |
| Rationale for change  |  | 
Reworded for clarity and because the storage of samples for PK analyses at the central laboratory should be limited to 5 years, where possible. The storage time needs to be in line with the local regulations.
   |
| Section to be changed |  | 5.6.1 Immunogenicity – Antidrug antibodies   |
| Description of change |  | 
Amendment of wording regarding storage of ADA samples
 
Original text:
 
The ADA samples will be discarded after the completion of the additional investigations and the Sponsor has approved this in writing, but not earlier than 5 years after the final CTR has been signed.
 
Amended text:
 
The ADA samples will be discarded after the completion of the additional investigations upon the Sponsor's written approval. The ADA samples may be destroyed 5 years after the final CTR has been signed, and in accordance with local regulation.
 |
| Rationale for change  |  | 
Reworded for clarity and because the storage of samples for biological analyses at the central laboratory should be limited to 5 years, where possible. The storage time needs to be in line with the local regulations.
   |
| Section to be changed |  | 7.3.1 Primary endpoint analysis
7.3.4 Safety Analysis  |
| Description of change |  | Correction of patient incidence   |

|                              |   |
|------------------------------|---|
|                              | 
Original text (section 7.3.1):
 
In addition, patient incidence and/or event incidence per 100 patient-years exposure will be provided. No formal inferential analyses are planned.
 
Corrected text:
 
In addition, patient incidence and/or event incidence per 1000 patient-years exposure will be provided. No formal inferential analyses are planned.
 
Corrected text (section 7.3.4):
 
In addition, for infections/serious infections, hypersensitivity reactions, drug-induced liver injury (DILI) and injection-site reactions, patient incidence and/or event incidence per 1000 patient-years exposure will be displayed.
 |
| Rationale for change  | Correction of an error in the original protocol to be in line with the protocol for the 1297.2 study.   |
| Section to be changed | 7.5.2 Efficacy endpoints  |
| Description of change | 
Revision of
 
Original text:
 
For DAS28 secondary endpoint, off-treatment assessments will not be taken into account. For missing data, LOCF will be applied on the component variables prior to the DAS28(ESR) score.
 
Other missing efficacy data will not be imputed. Further details will be given in the TSAP, including an additional analysis strategy using patients' off-treatment results.
 
Corrected text:
 
For missing data, LOCF will be applied on the component variables prior to the DAS28(ESR) score.
 
Other missing efficacy data will not be imputed. Further details will be given in the TSAP.
                |
| Rationale for change  | Correction of an error in the original protocol. No off-treatment efficacy data will be collected and no analysis regarding off-treatment efficacy will be  |

|  |  |                        |
|--|--|------------------------|
|  |  | done for study 1297.3. |
|--|--|------------------------|

**APPROVAL / SIGNATURE PAGE****Document Number: c03635799****Technical Version Number:2.0****Document Name: clinical-trial-protocol-revision-01**

**Title:** Long-term assessment of safety, efficacy, pharmacokinetics and immunogenicity of BI 695501 in patients with rheumatoid arthritis (RA): an open-label extension trial for patients who have completed trial 1297.2 and are eligible for long-term treatment with adalimumab

## MODIFICATION HISTORY

Unique Identifier for this Version	Date of the Document Version	Author	Significant Changes from Previous Authorized Version
1.0	22JUN2016		Not Applicable – First Version

---

Document: \\ieedc-nas01a\BIOSdata\Boehringer\_Ingelheim\BI\_695501\NVA96235\Biostatistics\Documentation\SAP\10  
v1.0\BI\_1297.3\_SAP\_22JUN2016\_v1.0

Author: Version Number: 1.0  
Version Date: 22JUN2016

Template No: CS\_TP\_BS016 – Revision 3  
Effective Date: 01May2012

Reference: CS\_WI\_BS005

---

## 1. INTRODUCTION

This document describes the rules and conventions to be used in the presentation and analysis of safety, efficacy, pharmacokinetics and immunogenicity data for Protocol 1297.3. It describes the data to be summarized and analyzed, including specifics of the statistical analyses to be performed.

This statistical analysis plan (SAP) is based on protocol version 2.0, dated 19 February 2016.

## 2. TRIAL OBJECTIVES

The objective of this trial is to provide long-term safety, efficacy, PK, and immunogenicity data on BI 695501 administered via prefilled syringe in patients with RA who have completed Trial 1297.2.

## 3. TRIAL DESIGN

### 3.1. GENERAL DESCRIPTION

This is a single-dose, open-label trial of BI 695501 with a 48-week treatment period in patients with RA continuing to receive methotrexate (MTX) within the dose range of the 1297.2 trial for at least 12 weeks after which point the MTX dose will be at the Investigators discretion. The trial will consist of a Screening visit 14 days prior to Day 1, a 48-week treatment period and a 10-week safety follow-up period (Week 58 visit). The Screening visit will be the Week 48 visit in Trial 1297.2. Patients will undergo up to 10 visits over the duration of the trial (58 weeks).

Patients who discontinue the trial medication early (and do not withdraw consent) should return to the site for an End of Treatment (EoT) visit equivalent to the Week 48 assessments as soon as possible after last trial medication administration. For patients who discontinue treatment early, a safety follow-up visit should be performed 10 weeks after the last administration of BI 695501.

It is anticipated that approximately 300 to 400 patients with moderately to severely active RA who have completed Trial 1297.2 will be eligible and willing to participate in this extension trial. Each patient who provides informed consent and meets all the inclusion criteria and none of the exclusion criteria will self-administer 40 mg of BI 695501 every 2 weeks by subcutaneous (SC) injection.

### 3.2. SCHEDULE OF EVENTS

Schedule of events can be found in Section “FLOW CHART” of the protocol.

---

Document: \\ieedc-nas01a\BIOSdata\Boehringer\_Ingelheim\BI\_695501\NVA96235\Biostatistics\Documentation\SAP\10  
v1.0\BI\_1297.3\_SAP\_22JUN2016\_v1.0

Author: Version Number: 1.0  
Version Date: 22JUN2016

Template No: CS\_TP\_BS016 – Revision 3  
Effective Date: 01May2012

Reference: CS\_WI\_BS005

### 3.3. CHANGES TO ANALYSIS FROM PROTOCOL

No change is planned.

## 4. PLANNED ANALYSES

### 4.1. DATA MONITORING COMMITTEE (DMC)

There will be no DMC for this trial.

### 4.2. FINAL ANALYSIS

All final, planned analyses identified in this SAP will be performed by Biostatistics following Sponsor Authorization of this Statistical Analysis Plan, Database Lock, and Sponsor Authorization of Analysis Sets.

## 5. ANALYSIS SETS

Agreement and authorization of subjects included/ excluded from each analysis set will be conducted prior to the database lock of the trial.

### 5.1. ALL SUBJECTS ENROLLED SET [ENR]

The all subjects enrolled (ENR) set will contain all subjects who provide informed consent for this trial.

### 5.2. ALL SUBJECTS ASSIGNED SET [ASD]

The all subjects assigned (ASD) set will contain all subjects in the ENR set who were assigned to trial medication in 1297.3.

For analyses and displays based on ASD, subjects will be classified according to randomized / re-randomized treatments of trial 1297.2.

---

Document: \\ieedc-nas01a\BIOSdata\Boehringer\_Ingelheim\BI\_695501\NVA96235\Biostatistics\Documentation\SAP\10  
v1.0\BI\_1297.3\_SAP\_22JUN2016\_v1.0

Author: Version Number: 1.0  
Version Date: 22JUN2016

Template No: CS\_TP\_BS016 – Revision 3  
Effective Date: 01May2012

Reference: CS\_WI\_BS005

### 5.3. FULL ANALYSIS SET [FAS]

The full analysis set (FAS) will contain subjects from the ASD set, who received at least one dose of trial medication in Trial 1297.3, and had data recorded for at least one DAS28 (Erythrocyte Sedimentation Rate [ESR] or C-reactive protein [CRP]) or ACR20 during the 1297.3 trial (for at least one composite variable at least one non-missing value should be present on at least one post-baseline visit. It is not required that all composite variables must be non-missing at the same post-baseline visit). Subjects will be classified according to randomized / re-randomized treatments of trial 1297.2.

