**FLOW CHART (CONT'D)**

| Visit   | 1                      | 2               | 3                      | 4  | 5               | 6   | 7               | 8               | 9                      | 10        |
|---|------------------------|-----------------|------------------------|----|-----------------|-----|-----------------|-----------------|------------------------|-----------|
| Week  | Screening  | Baseline        | 6          | 12 | 18  | 24  | 32  | 40  | 48
EoT  | 58
SFU |
| Day   | -14                    | 1               | 43                     | 85 | 127             | 169 | 225             | 281             | 337                    | 407       |
| Permitted visit window (days)                         | (±3)                   | ±1              | -                      | ±2 | -               | ±2  | -               | -               | ±2                     | ±2        |
| EFFICACY ASSESSMENTS                           |                        |                 |                        |    |                 |     |                 |                 |                        |           |
| Swollen and tender joint counts                       | X                      | X               |                        | X  |                 | X   |                 |                 | X                      |           |
| Patient's global assessment VAS          | X                      | X               |                        | X  |                 | X   |                 |                 | X                      |           |
| Physician's global assessment VAS                     | X                      | X               |                        | X  |                 | X   |                 |                 | X                      |           |
| HAQ-DI                                   | X                      | X               |                        | X  |                 | X   |                 |                 | X                      |           |
| SF-36 v2                                 | X                      | X               |                        | X  |                 | X   |                 |                 | X                      |           |

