### **3.3.4 Removal of patients from therapy or assessments**

#### **3.3.4.1 Removal of individual patients**

Patients who do not meet all of the inclusion criteria or who meet one or more of the exclusion criteria will not be enrolled in this extension trial. The primary reason for the screen failure will be recorded on the electronic Case Report Form (eCRF).

Patients have the right to withdraw from this trial at any time for any reason.

Two situations can occur in this trial and need to be documented accordingly, as follows:

1. An individual patient is to be withdrawn from the trial if:
  - The patient decides to discontinue participation in the trial by withdrawal of consent. In this case, no more investigations will be performed. The patient does not have to justify the decision.
2. Based on assessment by the Investigator, and after consultation with the trial medical advisor, an individual patient may be discontinued from treatment with the investigational compound if:
  - The patient needs to take concomitant drugs that interfere with the investigational product or other trial medication
  - The patient can no longer be treated with trial medication for other medical reasons (such as surgery, adverse or drug-related events, other diseases, or pregnancy)
  - Repeated protocol violation after documented discussion with the medical monitor
  - Lack of efficacy
  - The patient has an AE that is categorized as a serious infection. A serious infection is defined as infections requiring i.v. antibiotics or those that meet the regulatory definition of a SAE (including, but not limited to, systemic fungal infections, human immunodeficiency virus [HIV], HBV, HCV, infected joint prosthesis)
  - Patient lost to follow-up despite reasonable efforts to make contact with the patient

If a patient permanently discontinues trial medication for any reason, every effort should be made for the patient to attend the EoT Visit as soon after trial treatment discontinuation as possible. Every effort should be made for all patients who discontinue the trial treatment early, to return for a safety follow-up visit 10 weeks after the last dose of trial medication. For details of assessments to be performed at the Week 48 visit and the Week 58 visit, see [Sections 6.2.2](#) and [6.2.3](#), respectively.

For all patients the reason for withdrawal (e.g., AEs) must be recorded in the eCRF. These data will be included in the trial database and reported.

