#### Baseline, Visit 2 (Day 1)

Eligible patients will receive their first administration of trial medication on Day 1.

The following will also be performed/collected:

- Physical examination, including weight (kg) (see [Section 5.3.1](#))
- RF and anti-CCP antibodies
- Patient questionnaires: global VAS, HAQ-DI and SF-36 v2 (see [Section 5.2](#))
- Joint assessment (see Section 5.2)
- ESR and CRP
- Physician questionnaire: global VAS (see Section 5.2)
- Vital signs (blood pressure, pulse rate, respiratory rate, and body temperature; see [Section 5.3.2](#))
- Urine pregnancy test for women of child-bearing potential
- Laboratory testing (serum chemistry, hematology and urinalysis; see [Section 5.3.3](#))
- 12-lead ECG (see [Section 5.3.4](#))
- Previous and concomitant therapy (see [Section 4.2](#))
- Assessment of AEs (see [Section 5.3.6](#))
- Blood PPK samples (see [Section 5.4](#))
- Blood samples for the level of ADAs and nADAs (see [Section 5.6.1](#))
- Contact IRT and administration of trial medication
- Dispense trial medication

Patients will be instructed to accurately record the dates and times of BI 695501 dosing, and the occurrence of any AEs and use of concomitant medications, on the provided diary cards between the ambulatory visits.

The Investigator should plan with the patient when Visit 3 (Week 6) will occur and 3 syringes will be dispensed to the patient.

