### **7.3 PLANNED ANALYSES**

All patients treated with at least one dose of trial medication during the 1297.3 trial (Safety Analysis Set) will be included in the safety evaluations.

The Full Analysis Set (FAS) will be the basis for efficacy analyses. The FAS consists of all patients who received at least one dose of trial medication in Trial 1297.3 and had at least one DAS28 (ESR or CRP) or ACR20 measured during the 1297.3 trial.

The “All Enrolled Patients” analysis set will include all patients who provide informed consent for this trial.

For presentation of results in the report, three groups of patients will be created depending on treatments assigned in Trial 1297.2. The first group will consist of patients who were randomized to BI 695501 in Trial 1297.2 and will continue to receive BI 695501 in Trial 1297.3 but via self-administration. The second group will consist of patients who were initially randomized to receive US-licensed Humira® in Trial 1297.2, continue to receive US-licensed Humira® after Week 24 re-randomization in Trial 1297.2 and will transition to BI 695501 via self-administration in the Trial 1297.3. The third group will consist of patients who were initially randomized to receive US-licensed Humira® in Trial 1297.2, transitioned to BI 695501 following the re-randomization at Week 24 in the Trial 1297.2 and continue to receive BI 695501 in Trial 1297.3 but via self-administration. [Table 7.3: 1](#) gives an overview of the above-defined patient groups.

Table 7.3: 1 Patient groups for presentation of analysis results

| Patient group                              | 1  | 2            | 3            |
|---|-----------|---------------------|---------------------|
| Randomized treatment in Trial 1297.2              | BI 695501 | US-licensed Humira® | US-licensed Humira® |
| Re-randomized treatment in Trial 1297.2 (Week 24) | BI 695501 | US-licensed Humira® | BI 695501           |

The descriptive statistics for safety, efficacy and other endpoint will be presented for these three groups and overall for all patients combined.

Unless otherwise specified, baseline for this trial (1297.3) is defined as the baseline of Trial 1297.2 and all endpoints are those assessed in Trial 1297.3.

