### 7.5.2 Efficacy endpoints

Missing ACR20 data will be imputed using the last observation carried forward (LOCF) method. However, all patients who discontinue treatment, are lost-to-follow-up or have any severe violation related to any therapy that may significantly impact efficacy assessment ([Table 4.2.2.1: 1](#)) prior to the secondary endpoint assessment will be considered as a non-responder. This is referred to as 'NRI' (missing data imputation of primary analysis in 1297.2).

. For missing data, LOCF will be applied on the component variables prior to the DAS28(ESR) score.

Other missing efficacy data will not be imputed.

Further details will be given in the TSAP.

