### 6.2. BASELINE

Unless otherwise specified, baseline in Trial 1297.3 is defined as the last non-missing measurement taken prior to reference start date (including unscheduled assessments). In the case where the last non-missing measurement and the reference start date coincide, that measurement will be considered pre-baseline. Adverse Events (AEs) and medications commencing on the reference start date will be considered post-baseline.

For the analysis referring to the 1297.2 baseline, the baseline value as derived in 1297.2 will be used. All endpoints will be assessed using the 1297.2 baseline values. In addition, the following further endpoints will be assessed using the 1297.3 baseline values:

- DAS28 (ESR)
- ACR20 response criteria
- SF-36 v2

---

Document: \\ieedc-nas01a\BIOSdata\Boehringer\_Ingelheim\BI\_695501\NVA96235\Biostatistics\Documentation\SAP\10)v1.0\BI\_1297.3\_SAP\_22JUN2016\_v1.0

Author: Version Number: 1.0  
Version Date: 22JUN2016

Template No: CS\_TP\_BS016 – Revision 3  
Effective Date: 01May2012

Reference: CS\_WI\_BS005

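### The SAP full analysis set adds a post-baseline condition, so treated patients who leave before Week 12 with no later value drop out of the ACR20 denominator instead of counting as non-responders

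*SAP*

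**What the plan says.** Protocol 7.3 makes the FAS the basis for efficacy. A patient with at least one 1297.3 dose enters it if the patient "had at least one DAS28 (ESR or CRP) or ACR20 measured during the 1297.3 trial". The protocol does not ask that the measurement come after baseline.

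SAP 5.3 repeats this condition and adds in parentheses that "for at least one composite variable at least one non-missing value should be present on at least one post-baseline visit". Components may come from different visits. The clause does not say which baseline it means. SAP 3.3, on changes from the protocol, reads "No change is planned".

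SAP 6.2 sets the default 1297.3 baseline at the last available value before the first 1297.3 dose. It also places a value dated on the day of that dose on the pre-baseline side.

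SAP 15.2 analyses ACR20 at Week 48 on the FAS with a combination of non-responder imputation (NRI) and last observation carried forward. Under protocol 7.5.2 the non-responders are "all patients who discontinue treatment, are lost-to-follow-up or have any severe violation related to any therapy" with a likely effect on efficacy, when this happens before the endpoint assessment. Table 1 in SAP 15.2.2.2 gives the same outcome for early discontinuation whether or not ACR20 can be computed.

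**The concern.** NRI needs no on-treatment data: leaving early settles the outcome. A membership rule that asks for a later value before NRI is applied removes some of the patients for whom the rule settles the outcome most clearly. Those removed are all failures, so the reported ACR20 proportion moves in one direction only. The trial has no hypothesis test, so this proportion is itself the result for the endpoint. Because the SAP declares no change, a reader would assume that the denominator is the protocol's.

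**Working it through.** The plan states no figure to reproduce. The check compares the texts and then applies simple arithmetic.

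**1. Does Day 1 satisfy the protocol FAS?** Yes. The Flow Chart schedules joint counts, both global VAS scores, HAQ-DI, ESR and CRP at the 1297.3 Baseline visit. Protocol 6.2.2 says: "Eligible patients will receive their first administration of trial medication on Day 1". Every treated patient therefore attends a 1297.3 visit at which the DAS28 components are due.

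**2. Does Day 1 satisfy the SAP clause?** Not under the SAP 6.2 default, because a Day 1 value is pre-baseline. The Week 6 visit is for medication only, so the next scheduled efficacy assessment is Week 12 (Day 85).

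**3. Who has nothing after Day 1?** For consent withdrawal, protocol 3.3.4.1 says: "In this case, no more investigations will be performed". A patient lost before Week 12 may also have no further value. Other early discontinuers are asked to attend an end-of-treatment visit with the Week 48 assessments, and a follow-up visit 10 weeks after the last dose at which ESR and CRP are taken. One component value from either visit appears to be enough for SAP 5.3.

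**4. How would NRI classify those who left with no later value?** As non-responders, since they stopped treatment or were lost before Week 48.

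**5. Effect on the proportion.** Let R be the number of responders, N the number of treated patients and k the number excluded in this way. None of the k is in R.

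- All treated: R/N
- SAP FAS: R/(N − k)
- Ratio: N/(N − k) = 1/(1 − k/N)

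Inputs:
- N = 300 to 400 is the anticipated enrolment (protocol 7.7).
- k/N is not in the documents; 1% to 5% is assumed, to show a range.
- The ACR20 rate has no planning value. 86/114 = 75.4% comes from the 60-month open-label study of the reference product described in protocol 1.2 and is illustrative only; 50% and 85% are assumed to bracket it.

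Example: N = 300, k = 3, R = 0.754 × 300 = 226.3. Then 226.3/300 = 75.4% and 226.3/297 = 76.2%, a rise of 0.8 points.

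| Assumed k/N | k at N = 300 / 400 | Rise at 50% | Rise at 75.4% | Rise at 85% |
|---|---|---|---|---|
| 1% | 3 / 4 | 0.5 | 0.8 | 0.9 |
| 2% | 6 / 8 | 1.0 | 1.5 | 1.7 |
| 3% | 9 / 12 | 1.5 | 2.3 | 2.6 |
| 5% | 15 / 20 | 2.6 | 4.0 | 4.5 |

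Rises are in percentage points above the all-treated rate. They depend on k/N, not on N.

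**The case against.** **The baseline is not named.** Protocol 7.3 takes the 1297.2 baseline by default, and ACR20 itself is measured from it (SAP 15.2.1.2). If SAP 5.3 means that baseline, Day 1 is post-baseline, almost nobody is removed and the statement of no change is correct. This stands as an ambiguity. The SAP 6.2 default and the name of the Day 1 visit favour the other reading, and two programmers could build different sets from the same text.

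**NRI works inside the FAS.** Protocol 7.5.2 is an imputation rule, not a membership rule, and the protocol FAS has a data condition of its own. A reader might infer that the SAP contradicts the NRI rule. The documents do not go that far: on the default reading, the SAP set removes patients before the rule reaches them, and the protocol set would keep those with a Day 1 measurement.

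**Most early leavers need not be lost.** A reader might infer that early drop-outs in general are excluded. The end-of-treatment and follow-up visits, together with the one-value threshold, do not support that. On that threshold the SAP is looser than the protocol wording, which asks for a DAS28 or ACR20.

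**The consequence is limited and visible.** ACR20 is a secondary endpoint in a single-arm descriptive trial, and the primary endpoint uses the safety set. SAP 9 reports the safety-set and FAS counts, so a careful reader could see the gap and recompute the rate. This stands and keeps the point modest, but it does not correct the reported figure.

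**Conclusion.** The point holds in a limited form. On the SAP 6.2 default baseline, SAP 5.3 removes from the ACR20 denominator treated patients who leave before Week 12 with no end-of-treatment, unscheduled or follow-up value, and SAP 3.3 does not record this. Exclusion of these patients can only raise the Week 48 proportion.

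The rise is probably small: under 1 point at an assumed 1% share, for any ACR20 rate shown. A reader might infer from the lower rows of the table that a bias of several points has been shown. It has not. A 5% share would mean 15 to 20 treated patients with no later value, and nothing in the documents supports that number. Nor do they suggest that such losses would differ between the three 1297.2 treatment-sequence groups. The same formula applies within each group, but the group sizes are not given.

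The conclusion rests on reading post-baseline as after Day 1. On the 1297.2 reading there is almost no effect, and what remains is unclear wording.

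**What to change.** For the ACR20 NRI analysis, use all patients with at least one 1297.3 dose and count those without later data as non-responders. This goes slightly beyond the protocol FAS, since it would also keep a treated patient with no Day 1 measurement, so SAP 3.3 should say so.

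Alternatively, delete the parenthesis in SAP 5.3 so that a Day 1 measurement qualifies, as in protocol 7.3. That would also bring these patients into the DAS28 analysis, and SAP 15.2.2.1 should then say whether a Day 1 value may be carried forward to Week 48.

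If the clause is kept for other endpoints, name the baseline it refers to and record the difference in SAP 3.3.

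The cost is SAP wording and a change of denominator in the ACR20 outputs. No new data are needed. The downside is a slightly less favourable ACR20 figure.
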